#### **4.3.1. Treatment After Progression**

Subjects will be treated until PD (according to RECIST 1.1 by Investigator's assessment), unacceptable toxicity, study withdrawal, or death, whichever comes first. However, treatment may be continued beyond PD if there is evidence of clinical benefit per the Investigator and the subject is tolerating study treatment. The following clinical criteria should be met for subjects to continue to receive treatment beyond the Investigator-assessed progression:

- Absence of symptoms and signs indicating clinically significant progression of disease.
- No decline in performance status.
- Absence of symptomatic rapid disease progression requiring urgent medical intervention (eg, symptomatic pleural effusion, spinal cord compression).

Sponsor consultation is required before subjects initiate the treatment beyond progression. If this occurs, the subject will remain in the study and continue to be monitored according to the protocol schedule of assessments ([Table 2](#)).

#### **4.4. End of Treatment Visit**

The End of Treatment (EOT) Visit should be conducted within 30 days after the decision has been made to discontinue treatment. If this is scheduled for 30 days ( $\pm$  14 days) after the last dose, the results from these assessments may also be used for the 30-Day Safety Follow-up Visit. Subjects who discontinue treatment because of toxicity will continue with radiologic response assessments at the protocol-required schedule, until PD or initiation of new therapy with capture of radiologic evidence of PD if clinically feasible. The reason for treatment discontinuation will be documented and any treatment-related AEs or clinically significant abnormal laboratory values at that time will be followed until resolution or stabilization.

- Complete physical examination including weight.
- Blood samples for:

- CBC with differential.
- Serum chemistry panel and liver function tests, glucose, creatinine, BUN, total bilirubin, AST, ALT, alkaline phosphatase, serum albumin, sodium, potassium, calcium, chloride, bicarbonate, magnesium, and phosphorus.
- Urine pregnancy test.
- Tumor assessment: CT or MRI scan with IV contrast as appropriate (chest, abdomen, pelvis, and other regions of known/suspected involvement), unless known anaphylaxis to contrast or medically contraindicated as described in Section 9. If imaging was obtained within 2 weeks of the EOT Visit, imaging does not need to be repeated.
- Blood collection for PK and ADA serum samples.
- Blood collection for biomarker samples.
- Record AEs.
- Concomitant medications.
- **CCI**

For subjects continuing treatment following implementation of PA5, EOT assessments will be performed according to [Table 3](#).

#### **4.5. 30-Day Safety Follow-Up Visit**

A single Safety Follow-up Visit will occur 30 days ( $\pm$  3 days) after the last dose of study drug and will include:

- Complete physical examination including weight.
- Urine pregnancy test.
- Blood samples for:
  - CBC with differential.
  - Serum chemistry panel and liver function tests, glucose, creatinine, BUN, total bilirubin, AST, ALT, alkaline phosphatase, serum albumin, sodium, potassium, calcium, chloride, bicarbonate, magnesium, and phosphorus.
- Blood collection for PK and ADA serum samples.
- Concomitant medications.
- Record AEs.
- Collection of subsequent anti-cancer treatment.

If the EOT Visit occurs at the same time or within 14 days of the scheduled 30-Day Safety Follow-up Visit, the same assessments may be utilized for both visits.

For subjects continuing treatment following implementation of PA5, the 30-Day Safety Follow-up Visit assessments will be performed according to [Table 3](#).

#### **4.6. Treatment Discontinuation**

Subjects may discontinue the study drug under any of the following conditions:

- 1) Withdrawal of consent from further treatment with study drug.
- 2) Lost to follow-up (see Section [4.6.1](#)).
- 3) An AE that, in the opinion of the Investigator or the Sponsor, contraindicates further dosing.
- 4) Initiation of alternative anti-tumor therapy, including any other investigational product.
- 5) Pregnancy.
- 6) More than a 3-week dose delay from the planned treatment date due to treatment-related toxicity or 5-week dose delay for all other reasons.
- 7) PD without evidence of clinical benefit with continued therapy.
- 8) Subject non-compliance.
- 9) Suspension of the study by the Sponsor.
- 10) Death.
- 11) Investigator's or treating physician decision in the absence of any of the above.

Study drug discontinuation should not result in subject discontinuation from the study, and the subject should continue to be followed up in the study for disease progression and survival per Section [4.7](#). Reasons for discontinuation from the study are described in Section [4.8](#).

If a subject discontinues study treatment (eg, as a result of an AE), every attempt should be made to keep the subject in the study and continue to perform the required study-related follow-up procedures (see Section [4.7](#)). If this is not possible or acceptable to the subject or Investigator, the subject may be withdrawn from the study.

#### **4.6.1. Lost to Follow-up**

A subject will be considered lost to follow-up if the subject repeatedly fails to return for scheduled visits and is unable to be contacted by the study site.

The following actions must be taken if a subject fails to return to the clinic for a required study visit:

- The site must attempt to contact the subject and reschedule the missed visit as soon as possible, counsel the subject on the importance of maintaining the assigned visit schedule and ascertain whether the subject wishes to and/or should continue in the study.
- Before the subject is deemed lost to follow-up, the Investigator or designee must make every effort to regain contact with the subject (where possible, 2 telephone calls, and if necessary, a certified letter to the subject's last known mailing address or local equivalent methods). These contact attempts should be documented in the subject's source documents.
- Should the subject continue to be unreachable, the subject will be considered lost to follow-up.

For subjects who are lost to follow-up, study staff may use public records (eg, public health records) to obtain information about survival status where allowable by local regulation.

#### **4.7. Safety/End of Treatment and Survival Follow-up**

After discontinuation of treatment (see Section 4.6), all subjects must complete an EOT Visit 30 days after the last dose of study drug and a 30-Day Safety Follow-up Visit (Table 2). Subjects will then be followed every 12 weeks for survival, unless the subject explicitly indicates a desire to forego survival follow-up to their study Investigator. Subjects will be followed until death, withdrawal of consent, lost to follow-up, Sponsor-terminated study or completion of survival follow-up (24 months after the last subject is dosed), whichever occurs first. This follow-up assessment may be conducted by telephone or in-clinic visit and will include documentation of any subsequent therapy for their cancer.

For subjects who are lost to follow-up, study staff may use public records (eg, public health records) to obtain information about survival status where allowable by local regulation.

Following implementation of PA5, subjects who previously discontinued treatment will no longer be followed for survival follow-up and subsequent therapy and will discontinue the study as per sponsor's decision.

#### **4.8. End of Study**

The end of the study for a subject's participation occurs when they have completed all periods of the study including long-term or survival follow-up due to the following reasons: death, the subject withdraws consent, there is documented loss to follow-up of the subject, or the Sponsor terminated the study, whichever comes first.

Please note, the End-of-Study page is also expected to be entered into the Electronic Data Collection (EDC) system once a subject completes the study even if there was no death event, withdrawal of consent, or loss to follow-up. The End-of-Study page is required to be completed in addition to the End-of-Treatment page.

Following implementation of PA5:

- Subjects may continue treatment as part of the study, for as long as they are deriving clinical benefit. After they meet one of the criteria for treatment discontinuation (Section 4.6), they will have an EOT visit and a 30-Day Safety Follow-up Visit. There will be no additional assessments including survival follow-up and subsequent therapy collection.
- Subjects will have the end of study at the same time as the EOT visit (Section 4.4). However, if at the time of an EOT visit, subjects have unresolved AEs, the end of study for that subject may be delayed until all AEs have been resolved or stabilized per Section 10.2.2.1.

The end of the entire study for all subjects is defined as the date on which the last subject remaining on study completes the last study visit/call/survival follow-up or when the Sponsor decides to end the study. The Sponsor reserves the right to terminate the study at any time for any reason (including safety).

At the completion of the study, subjects who are deriving benefit from sacituzumab govitecan monotherapy may continue to receive treatment in a rollover study (Study IMMU-132-14) in locations where the study is available. This rollover study is designed to provide continued access to sacituzumab govitecan for eligible subjects who have previously participated in a Gilead-sponsored parent study, who are tolerating sacituzumab govitecan, have no evidence of PD, or are still deriving clinical benefit despite progression (as assessed by the Investigator). Subjects may receive the dose of sacituzumab govitecan currently receiving in the parent study at the time of consenting to participate in the rollover study, if applicable.

CCI

[REDACTED]

## **5. STUDY EVALUATIONS**

All subjects must be dosed within 28 days of providing written informed consent. No subject may be dosed until the Sponsor or their representative has approved the eligibility packet. Clear documentation as to the reason the subject was not dosed should be provided on the relevant eCRF. Unless otherwise specified, visit windows are permitted either 1 day before or + 2 days after scheduled visits and  $\pm$  7 days for response assessments. Treatment delays for reasons other than required for resolution of treatment-related toxicity are not permitted.

CCI

CCI

CCI

CCI

CCI

**Table 3. Modified Schedule of Assessments/Study Calendar (After Implementation of PA5)**

Visit	Treatment		EOT Visit b	30-Day Safety Follow-up Visit c
Cycle	ALL Cycles			
Day a	1	8		
Weight d	X		X	X
Physical examination e	Per standard of care		X	X
Vital signs f	As needed			
Study drug administration	X	X		
Urine Pregnancy test (if applicable) g	X		X	X
Serum Follicle-Stimulating Hormone (FSH) h	As needed			
Hematology i	X	X	X	X
Serum chemistry including liver function tests j	X	X	X	X
Tumor assessment (CT or MRI scan) k	Per standard of care			
AE reporting l	X	X	X	X
Prior/concomitant medications	X	X	X	X
Subsequent anti-cancer treatment				X

Abbreviations: AE = adverse event; ALT = alanine aminotransferase; ANC = absolute neutrophil count; AST = aspartate aminotransferase; BUN = blood urea nitrogen ; CBC = complete blood count; CT = computed tomography; eCRF = electronic case report form; EOT = end of treatment; MRI = magnetic resonance imaging; PA5 = Protocol Amendment 5; SAE = serious adverse event.

- a Unless otherwise specified, visit windows are within -1 to +2 days of the schedule visits and  $\pm 7$  days for response assessments.
- b The EOT Visit should occur within 30 days of the decision to discontinue treatment. If the EOT Visit and 30-Day Safety Follow-up Visit occur within 14 days of each other, the same assessment results may be utilized for both study visits.
- c The Safety Follow-up Visit should be conducted 30 days ( $\pm 3$  days) after the last dose of study drug.
- d During treatment, subject's body weight will be measured on Day 1 of each treatment cycle (or more frequently if the subject's body weight changed by >10% since the previous administration), at the EOT Visit, and at the 30-Day Safety Follow-up Visit.
- e Complete physical examinations will be performed at the EOT Visit and the 30-Day Safety Follow-up Visit. At study visits during the Treatment Phase, physical examinations should be performed per institutional practice.
- f Collection of vital signs will be needed in the event of suspected infusion-related reaction. Vital signs will include blood pressure, heart rate, pulse, respiratory rate, and body temperature and will be taken after the subject has been resting for at least 5 minutes.

- g In females of childbearing potential, pregnancy testing will be performed on Day 1 of each treatment cycle, and every 28 days after the last dose of study drug up to 6 months after the last dose of study drug per the duration of required contraception, as described in Appendix [17.5](#). Testing during the posttreatment period may be performed at home and the result is to be self-reported by the subject. If the urine test is positive or equivocal, a confirmatory serum pregnancy test will be required.
- h Conduct as needed per Appendix [17.5](#).
- i CBC with differential for all subjects is required at Days 1 and 8 of each cycle, and the EOT Visit and 30-Day Safety Follow-up Visit. Hematology tests may be performed and reviewed up to 24 hours prior to scheduled study treatment administration. See Section [7.5.2.5](#) for when sacituzumab govitecan should be administered based on ANC.
- j Serum chemistries include liver function test, glucose, creatinine, BUN, total bilirubin, AST, ALT, alkaline phosphatase, serum albumin, total protein, sodium, potassium, calcium, chloride, bicarbonate, magnesium, and phosphorus. Serum chemistries are required in all subjects at Days 1 and 8 of every cycle, the EOT Visit, and 30-Day Safety Follow-up Visit. These laboratory assessments may be obtained more frequently at the discretion of the treating physician if abnormal results warrant follow-up. Serum chemistries may be performed and reviewed up to 24 hours prior to scheduled study treatment administration.
- k Subjects who continue treatment following implementation of PA5 will be expected to have scans performed per standard of care, as indicated by local practice. Tumor response data will no longer be collected for this study; however, disease status should still be monitored by the treating physician to determine if progression has occurred, and whether the subject is continuing to derive clinical benefit.
- l All AEs and SAEs must be reported in eCRF and to Gilead Global Patient Safety from first dose of study drug until 30 days after last dose of study drug or initiation of alternative therapy for underlying disease in accordance with instructions in Section [10.2.5](#). SAEs that occur after initiation of a new anticancer therapy will not be reported.

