### **10.2.4. Reporting Exposure During Pregnancy**

Pregnancy occurring in a female subject from start of the study and throughout the study (including the post study drug follow-up period) or within 6 months after the end of treatment, whichever is longer, should be reported to the Sponsor or the Sponsor’s designee on the Pregnancy Form within 24 hours of the Investigator’s becoming aware of the event. Pregnancy occurring in female partners of male subjects from start of the study and throughout the study (including the post study drug follow-up period) or within 3 months after the final dose, whichever is longer, should be reported to the Sponsor or the Sponsor’s designee within 24 hours of becoming aware of the event.

The Investigator should counsel the subject, and in the case of a male subject, the subject’s partner, regarding the risks of continuing with the pregnancy and the possible effects on the fetus.

If the female partner of a male subject becomes pregnant, the Investigator should obtain informed consent from the pregnant partner prior to monitoring the pregnancy, so that information regarding the pregnancy outcome can be reported to the Sponsor.

Information regarding the pregnancy should include estimated date of conception, duration of study drug exposure (or number of days/months after treatment discontinuation) as of the estimated conception date, expected delivery date, date of last menstrual period, all concomitant medications (including recreational drug use such as alcohol, tobacco, and illicit drugs) and other maternal medical conditions.

The Investigator should make every effort to follow the subject (or female partner of a male subject) through the resolution of the pregnancy, ie, delivery or pregnancy termination. If the pregnancy results in abortion (spontaneous or induced), or premature birth, or if the infant is born with a congenital anomaly, these events are considered SAEs and should be reported as described in Section [10.2.5](#). The outcome of all pregnancies must be reported to the Sponsor,

even for normal births. The condition of the infant at birth should be reported, including any anomalies, and the infant should be followed until 3 months of age and any illnesses should be reported.

All information regarding the pregnancy in a female subject or female partner of a male subject and the infant should be reported on the Pregnancy Form.

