#### **b.      Contraception Requirements for Female Subjects of Childbearing Potential**

The inclusion of female subjects of childbearing potential requires the use of highly effective contraceptive measures that have a failure rate of less than 1% per year. Subjects must have a negative serum pregnancy test during screening and a negative urine pregnancy test is required at baseline prior to study treatment administration on Cycle 1 Day 1 (C1D1). The baseline urine pregnancy test does not need to be conducted if the screening pregnancy test was performed within 72 hours before study treatment administration on C1D1. Pregnancy tests will be performed thereafter on Day 1 of each treatment cycle starting from Cycle 2 through last cycle.

and every 28 days after the last dose of study drug until the end of contraception requirement. If a urine test is positive or equivocal, a confirmatory serum pregnancy test will be required.

Duration of required contraception for female subjects in this clinical study should start from the Screening Visit until 6 months after the last dose of study drug.

Female subjects must agree to 1 of the following contraceptive methods:

Complete abstinence from intercourse of reproductive potential. True abstinence is an acceptable method of contraception only when it is in line with the subject's preferred and usual lifestyle.

Or

Consistent and correct use of 1 of the following methods of birth control listed below:

- Nonhormonal intrauterine device (IUD)
- Hormonal IUD (must be used in conjunction with a barrier method)
- Bilateral tubal occlusion (upon medical assessment of surgical success)
- Vasectomy in the male partner (upon medical assessment of surgical success)

Or

Female subjects who wish to use a hormonally based method must use it in conjunction with a barrier method, preferably a male condom. Hormonal methods are restricted to those associated with the inhibition of ovulation. Hormonally based contraceptives and barrier methods permitted for use in this protocol are as follows:

- Hormonal methods (each method must be used with a barrier method, preferably male condom)
  - a) Oral contraceptives (either combined or progesterone only) (see Appendix 17.6 for a list of UGT1A1 inducers and Section 7.6.)
  - b) Injectable progesterone
  - c) Subdermal contraceptive implant
  - d) Transdermal contraceptive patch
  - e) Contraceptive vaginal ring

- Barrier methods (each method must be used with a hormonal method)

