## **5) Procedures to Be Followed in the Event of Pregnancy**

Patients assigned female at birth will be instructed to notify the Investigator if they become pregnant or suspect they are pregnant at any time from start of the study and throughout the study (including the post study drug follow-up period) or 6 months after the last dose of study drug, whichever is longer. Study drug must be discontinued immediately upon consultation with the medical monitor.

Patients assigned female at birth whose partner has become pregnant or suspects she is pregnant from start of study and throughout the study (including the post study drug follow-up period) or 3 months after the last study drug dose, whichever is longer, must also report the information to the Investigator. Instructions for reporting pregnancy, partner pregnancy, and pregnancy outcome are outlined in Section [10.2.4](#).

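### After Amendment 5 the protocol requires pregnancy tests to 6 months after last dose but ends assessments at the 30-Day visit, and Appendix 17.5 addresses the partner-pregnancy duty to the wrong sex

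*Protocol*

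**What the plan says.** **Testing after the last dose.** Table 3 is the schedule for subjects who stay on treatment after PA5. Its footnote g asks for a pregnancy test in females of childbearing potential on Day 1 of each cycle and then "every 28 days after the last dose of study drug up to 6 months after the last dose of study drug". On the post-treatment tests it adds: "Testing during the posttreatment period may be performed at home and the result is to be self-reported by the subject". Appendix 17.5, item 2b, sets the same interval, "every 28 days after the last dose of study drug until the end of contraception requirement", and says that the contraception period "should start from the Screening Visit until 6 months after the last dose of study drug".

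**End of assessments.** The Synopsis and Section 4.8 give a subject who stops treatment after PA5 two visits, EOT and 30-Day Safety Follow-up, and then state: "There will be no additional assessments including survival follow-up and subsequent therapy collection". Both put the subject's end of study at the EOT Visit. The only reason given for delaying it is an unresolved adverse event. The Table 3 grid has no column beyond the 30-Day visit. Under Sections 3 and 4.7, subjects already off treatment when PA5 takes effect are discontinued from the study.

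**Partner pregnancy.** The second paragraph of Appendix 17.5, item 5, is addressed to "Patients assigned female at birth whose partner has become pregnant or suspects she is pregnant", with a window of 3 months after the last dose. Section 10.2.4 concerns female partners of male subjects and uses the same window: a partner pregnancy in the study "or within 3 months after the final dose, whichever is longer, should be reported to the Sponsor". Item 3 of Appendix 17.5 sets 3 months as the male contraception period.

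**The concern.** Appendix 17.5 describes the drug as contraindicated in pregnancy and names exposure through seminal fluid as a potential risk to an embryo or fetus. Follow-up after the last dose is how such exposures come to light.

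Two things look wrong. First, the PA5 text contains a testing rule that runs for 6 months and a closing rule that stops at about 1 month, and neither refers to the other. A site that applies Section 4.8 closes the record. A site that applies footnote g waits about five more months for results, with no scheduled contact at which to receive them. Second, the paragraph meant to make a patient report a partner's pregnancy does not name the patients it concerns. The 24-hour reporting duty in Section 10.2.4 starts only when the Investigator becomes aware, so it depends on the patient having been told to speak up.

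**Working it through.** The protocol states no figure to reproduce. The check is a comparison of texts and one count.

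**1. The post-PA5 passages side by side**

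| Place | After treatment stops |
|---|---|
| Table 3, footnote g | Test every 28 days to 6 months after last dose; home test with self-report possible |
| Appendix 17.5, item 2b | Same interval, to the end of the contraception period (6 months) |
| Table 3, grid | Urine test at EOT and at the 30-Day visit; no later column |
| Synopsis and Section 4.8 | EOT and 30-Day visits, then nothing further; end of study at EOT unless adverse events are unresolved |
| Sections 3 and 4.7 | Subjects already off treatment leave the study; the 6-month window is not mentioned |

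All of this is current text and does not rest on the amendment history. The adverse-event exception does not cover routine pregnancy testing.

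**2. Number of tests affected**

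- Length of the window: 6 × 30.4375 = 182.6 days, using the SAP's own conversion of days to months.
- Tests implied: 182.6 / 28 = 6.5, so 6 complete intervals, on Days 28, 56, 84, 112, 140 and 168.
- The 30-Day visit is at 30 ± 3 days after the last dose, that is, Days 27 to 33. It can cover the Day 28 test.
- Tests after that visit: 6 − 1 = 5 (Days 56 to 168), or 5/6 = 83%.

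The count takes the 30-Day visit as the last contact, which agrees with Section 4.7, where EOT falls 30 days after the last dose. Section 4.4 and Table 3 instead allow EOT up to 30 days after the decision to stop. If a late decision moved EOT to about Day 56, one more test could coincide with it, leaving 4 of 6.

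**3. The partner paragraph**

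- The first paragraph of item 5 tells patients assigned female at birth to report their own pregnancy, with a 6-month window.
- The second paragraph names the same population for a partner's pregnancy, with a 3-month window.
- Section 10.2.4 and item 3 both tie the 3-month window to male subjects.
- The window and the pregnant partner point to men, so the population appears to have been carried over from the paragraph above. As worded, item 5 gives male patients no instruction to notify the Investigator.

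**The case against.** The best reply is that the specific rule qualifies the general one. The sentence in Section 4.8 is mainly about ending survival follow-up and the collection of later therapies. Footnote g was written for the post-PA5 schedule, deals only with pregnancy, and allows home testing, which needs no visit. The pregnancy row of the grid carries footnote g, so grid and footnote are meant to be read together. On this view only a cross-reference is missing. The partner paragraph is a slip that Section 10.2.4, which item 5 itself cites, already makes good.

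Much of this stands, and it rules out three stronger readings that a reader might infer:

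- **That testing is forbidden after the 30-Day visit.** The protocol says no more assessments will follow; it does not prohibit them, and footnote g is itself post-PA5 text.
- **That pregnancies would be missed, or that most of the 6 months goes unobserved.** Item 5 tells female subjects to notify the Investigator of a pregnancy through the study or 6 months after last dose, whichever is longer, and Section 10.2.4 keeps the reporting duty open beyond study exit. A route for notifying a pregnancy exists; a scheduled route for the test results does not. The 5 of 6 holds only if Section 4.8 is taken to override footnote g.
- **That most of the study is affected by the partner paragraph.** The planned proof-of-concept cohorts other than endometrial add up to 30 + 30 + 30 + 40 = 130 of 165. That is no more than a ceiling on planned enrolment in those cohorts: it includes women, and men without a partner of childbearing potential. Estimated last enrolment was 30 May 2023 and PA5 is dated 17 December 2024, so the number still inside a 3- or 6-month window may be small.

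The reply does not remove the inconsistency. Nothing in Section 4.8 or the Synopsis exempts pregnancy follow-up, and the one exception they give is for something else. Nothing is said about subjects discontinued at PA5 while still inside the window. Section 10.2.4 binds the Investigator and does not instruct the male patient.

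**Conclusion.** The point holds as an internal inconsistency in pregnancy safety follow-up, with two parts.

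1. After PA5, the testing rule and the closing rule conflict. If Section 4.8 is followed, 5 of the 6 tests implied by footnote g come after the last scheduled assessment, given a 30-Day visit that covers the first test and an EOT Visit no later than about that time. Pregnancies in this period could go unreported; the documents do not support saying that they would.
2. Item 5 of Appendix 17.5 names the wrong population for partner pregnancy and so leaves male patients without an instruction there.

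The documents do not give the number of women of childbearing potential, or of men with such partners, who are affected. No endpoint, sample size or statistical analysis depends on this. It should be corrected because it concerns embryo-fetal safety and the correction is cheap.

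**What to change.** - Reconcile the Synopsis, Sections 3, 4.7 and 4.8, and the Table 3 grid with Table 3 footnote g and Appendix 17.5, item 2b. The protocol should state which rule applies after PA5, including for subjects discontinued at PA5 who are still within 6 months of their last dose. Which rule that is remains for the sponsor to decide.
- If post-treatment results are required, state how the site receives them and how this fits with the subject's end of study.
- Align the population named in the second paragraph of Appendix 17.5, item 5, with Section 10.2.4 and with item 3 of the appendix.

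The cost is a change of protocol wording and, depending on the rule chosen, a later end-of-study entry for what may be a small subset of subjects.
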